The Bangladesh Integrated Nutrition Project (BINP) of the Government of Bangladesh has started showing reduction in malnutrition of women and children under two years of age in last 3 years of it's activities. Moderately malnourished children form a large proportion of children in the community. With success of the BINP this proportion is farther increasing as severely malnourished children are improving and "graduating" to the moderately malnourished category. Recent operations research of BINP shows that it is possible to reduce moderate malnutrition substantially through a specific package of intensive nutrition education. (INE). That was a demonstration study to test the efficacy of the approach on a relatively small number of children with intensive intervention. There is now an urgent need to define an effective and feasible means applicable in a larger population in the country. A study will be therefore conducted in 4 division of BINP thanas of Bangladesh over an 18-month period. Moderately malnourished children will be in management intervention and mildly malnourished and well-nourished infants will be in preventive intervention group. For management intervention, a total of 750 moderately malnourished will be randomized to receive either intensive nutrition education or less intensive education. For preventive purpose, 380 mildly malnourished children of 6 months to 2 years of age and 100 well nourished infants of 6 to 9 months of age will receive either less intensive education or no education. Infants between 6 to 9 month ages will be brought under less INE to ensure their complementary feeding practice. Care givers of one group of mildly malnourished children and one group of 6-9 month old infants will not receive any education to serve as controls. Focus Group Discussion (FGD) based INE will be conducted taking into consideration of geographical variation for an in-depth understanding of culture. Focus group discussion will be held with mothers to discuss beliefs, food habits and feeding practices of these children. An anthropologist and a nutritionist will jointly develop the nutrition education package. INE on child caring and on food security and disease control. Mothers of the first intervention group will receive intensive nutrition education and motivation for childcare, complementary food demonstration, and household food mobilization for child feeding twice weekly for first three months, which will be then reinforced once in a week for the last three months of intervention. The less intensive intervention group will receive nutrition education with the same components twice a week for the first month then once a week for two months and then twice monthly for the last three months of intervention. INE will be given for a total of 6 months. An observation will be done to identify for sustainability effect for an additional period of 6 months. Their weight and length gain will be recorded. The Community Nutrition Promoter (CNP), Community Nutrition Organizer (CNO), women's group and village nutrition committee will be involved in motivating and

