
ensuring child caring practices. Data on morbidity will be collected and necessary medical advice for referral to the health centre will be given equally to each group. The CNP and CNO's time will be mapped and will be asked to adopt study messages to examine the practicality. Data collection, counseling on child caring practice, food demonstration and nutrition education using IEC will be organized and supervised by project staff. It is assumed that if the intervention is successful, and once the nutritional status improves, they are likely to maintain good health. The IEC on dietary practice will be communicated to the VNMC (village nutrition management committee) members for further preventive measures. Data on cost effectiveness of the nutrition education strategies will be collected by a health economist. Data will be analyzed for change in nutritional status from moderate to mild malnutrition or normal nutrition and proportions of children continuing complementary feeding will be compared between the intensive and less intensive intervention and control groups. It is expected that the results of the study will help define the effectiveness of our nutrition education package to prevent and reduce moderate malnutrition existing in large proportion of children in setting with different geographical, and cultural and feeding practices.

KEY PERSONNEL (List names of all investigators including PI and their respective specialties)

Name	Professional Discipline/ Specialty	Role in the Project
1. [name]	Scientist, ICDDR, B	Principal Investigator
2. [name]	Director, CSD, ICDDR,B	Co-Principal Investigator
3. [name]	Senior Medical officer ICDDR, B	Co-Investigator
4. [name]	BRAC, Bangladesh	Collaborative investigator

DESCRIPTION OF THE RESEARCH PROJECT

Hypothesis to be tested:

Concisely list in order, in the space provided the hypothesis to be tested and the Specific Aims of the proposed study. Provide the scientific basis of the hypothesis, critically examining the observations leading to the formulation of the hypothesis.

Hypothesis

- a. Less intensive nutrition education including food demonstration at the community level will be equally effective as intensive nutrition education for the prevention and reduction of moderate malnutrition.
- b. The effect of less intensive nutrition education given over a period of 6 months will sustain during the following six months without any intervention.

Specific Aims:

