- (4) The fourth group will be controls for the preventive group with mildly malnourished children and well nourished 6-9 month aged infants who will not receive any education.

Moderately malnourished children will be included to improve their nutritional status into better nutrition and well nourished and mildly malnourished children will be included to prevent their fall as well as improve in nutrition status.

Details of the nutrition counseling and demonstration of food are given in annex 1.

There will be modification of nutrition education after baseline FGD studies on food perception. The base line weight and length of each child will be recorded. Weight and length will be taken each month for a period of 6 months. Project workers will also take information on anthropometry from the GMP sessions. The main responsibility of education will remain with the health assistant. CNP timing will be mapped and their special training manual will be prepared. They will be trained in different sessions to educate the mothers groups. The sessions with moderately malnourished children and their parents will be organized in consultation with village nutrition management committee (VNMC). The counseling will be based on pictorial or written script in Bangla. Required number of sessions will be planned for increasing the ability to recognize moderately malnourished children. The feasibility will be seen through exploratory meeting with VNMC and moderately malnourished children's mothers.

In the intervention area, **complementary food** will be prepared and demonstrated by the nutritionist and health assistants. Feeding will be encouraged in groups at the community level for initial one month and then it will be encouraged to do at home with supervision of the women support group and health assistants.

Sample size calculation:

Sampling frame: The study subjects will be under 2 years of age and will be recruited from the growth-monitoring program at CNC. Of the total population about 4.5% are under 2 years at a given time. From this population about 10% show growth faltering and come to the CNC for supplementary feeding as the part of the BINP activities. About thirty eight percent children under 2 years of age suffer from moderate malnutrition, about 43.7% are mildly malnourished and about 13.7% are normal according to recent baseline report of BINP.

Sample size for management study group:

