CNP and CNO's will be asked for their time to learn the specific nutrition education that has proven to be successful for improving nutrition status and they will be involved to pick up the work schedules of the research team. After the first three months of study, adaptation process will begin. If time is available CNP's will take over the health assistant's work and CNO's will take over supervisor's work by end of 6 months and will replicate in more CNC's.

Time will be planned with CNO and CNP's to define their role in nutrition education. The current

study with knowledge of the previous one will identify specific knowledge base that helps behavior change communication of mothers in feeding appropriate food and frequency, referral during illness, and caring practices. A review of the BINP training manual will be done to find adjustment of the specific messages based on our messages on the preventive and management approaches for introduction of complementary feeding. An initial standardization of CNP sessions with mothers will be done with project investigators and field staff. Supervisory level adaptation of monitoring the quality of CNP and CNO work will be planned and accommodated. It remains to see the actual operations taking place in context of time constraint of CNP's in their daily work schedules. The details on following areas will be worked out with the NGO implementing in Thanas before planning of adaptation can be actually begun.

1. Availability of CNP and CNO time
2. Training of CNP and CNOs
3. Monitoring / Supervision
4. Evaluation of the work

Cost Effectiveness of the Alternative Strategies to address moderately malnourished children

Add in specific objective section the following:

5. To assess the cost-effectiveness of the two alternative strategies to prevent and reduce moderate malnutrition in 6-24 months old children.

Add in the conceptual framework section:

In order to assess the cost-effectiveness of the two alternative strategies, the costing of the intervention activities will be undertaken.

To ensure that all relevant resources used for the alternative intervention strategies, it will be necessary to observe outputs (effectiveness measures) being produced and then try to link the inputs/resource used in the production of specific outputs.

Data will be collected to determine the following costs while undertaking the intervention.

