For preparation of food and taking care of the child, mothers' time was critically important e.g. during harvesting period, mothers could find little time for cooking supplementary food as well as make the child feed by herself. Mothers cooked extra khichuri for children on 3-4 days a week. Alternate food mixes taught by health assistants were given from family pots during the weekdays. Many of the poor families could manage only one meal a day and could not afford to buy varieties and ideal ingredients to prepare complementary food. With frequent nutrition education, parents purchased dietary items which mothers

initially resisted because they perceived not essential for better child growth. Mothers reported that with the improvement in nutritional status of moderately malnourished children, their husband took more initiative to buy more special foods for their children. These items included soybean oil (usually cooking was done with mustard oil), eggs, lentils/dhal and different colored vegetables. Superstitions and food taboos on some food items were almost removed in the intervention groups.

Some improvements were also observed in the control group, which attributed to all or some of the following reasons: a) Two weekly nutrition education was given to mothers of the moderately malnourished children by CNPs and CNOs of the implementing NGO. b) The NGO workers (CNO/CNP) adopted and used specific messages from instruction of our health assistants at the field level. C) The baseline data on prevalence of malnutrition was collected immediately after the flood and therefore there was natural recovery in the first month in all the study groups after flood period. D) The study period covered the harvesting season enabling a better food intake in all groups.

Children from all groups were followed up for an additional period of 3 months after the intervention. The improvement weight gain continued steadily only in the intervention groups.

We concluded that, the substantial reduction in moderately malnourished children through nutrition education and SF has significant potential to reduce this staggering problem. Further research is needed to define the intensity of education needed to achieve sustained improvement.

[name], Hope this is helpful!

Reviewer - I

Best,
[name]

May 1999

TO: [name]

FROM: [name]

SUBJECT: Your O.R. Draft on Feasible Means to Address Moderately Malnourished Children

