Q.4. Objectives: The section containing hypothesis, conceptual framework and objectives should be rewritten. The objectives lack clarity and focus and are not in agreement with the design. Conceptual framework should be drawn as diagram.

Ans.4. a . Hypotheses and objective is modified on **page 6**.

b. Conceptual framework has been given as diagram on **page 12**.

Q.5. Materials and methods: Some revision is needed. This section will be more clearer if the content can be grouped, for example, SITE SELECTION, SAMPLE SIZE CALCULATION, SUBJECT SELECTION AND RANDOMIZATION, INTERVENTION, PERIOD OF STUDY (justification on seasonal effect).

Ans.5. Material and methods has been grouped and made clearer on **page 13**.

In regard to the method used, why not involve the assessment of Knowledge Attitude and Practice or KAP? Based on the proposed method and design as such, there is NO component to evaluate sustainability or cost-effectiveness, the investigators must decide whether to include these component or not.

The design will fully permit KAP result in beginning & all end of the study. Cost effectiveness study is not a direct objective of the study.

Q.6. Another point that needs clarification in the METHOD section is about WHO, HOW and HOW FREQUENT the Intensive or less intensive Nutrition education will be carried out. Some

information is provided in Annex I which should be included in the METHOD. Data management should consider that certain incomplete data may be corrected in the field and NOT to wait for reporting to the investigators which could be too late!

Ans.6. WHO, HOW and HOW FREQUENT the intensive or less intensive nutrition education will be carried out have been mentioned in the method section (**page:13**).

Q.7. Significance of the study: The design of this study at present does not address SUSTAINABILITY. Another issue of strengthening health supportive system and personnel needs to be brought up which is not within the scope of this study but may affect the study results.

Ans.7. Sustainability is not included in the objectives. But 6 months of observation will allow measuring it to a greater strength the adoption of the nutrition education by CNP will test more of sustainability through regular counseling.

8. Investigator's experience: It is not clear and does not reflect research experience of the principle investigators and team.

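### The conditional takeover of education by CNPs at month 6 contradicts the intervention-free follow-up that hypothesis (b) needs, and replication is not barred from the no-education CNCs

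*Protocol*

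**What the plan says.** Months are counted here from the start of education.

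- **Hypothesis (b):** "The effect of less intensive nutrition education given over a period of 6 months will sustain during the following six months without any intervention".
- **Project Summary:** after six months of education, "An observation will be done to identify for sustainability effect for an additional period of 6 months". The time frame chart places this phase after three intense and three reinforcement months, and Data Analysis treats it as a separate period.
- **Design of the project:** the health assistants carry the main responsibility for education.
- **Adaptation process of the CNPs and CNOs:** "After the first three months of study, adaptation process will begin". Then: "If time is available CNP's will take over the health assistant's work and CNO's will take over supervisor's work by end of 6 months". The same sentence adds replication in more CNCs, without naming them or giving a date relative to the end of observation.
- **Answer to question 7 of the second external reviewer:** "6 months of observation will allow measuring it to a greater strength the adoption of the nutrition education by CNP". The sentence continues that this adoption will further test sustainability by way of regular counselling.
- **Selection and randomization procedure:** each of the 8 unions has five CNCs with education and one without. The 8 extra CNCs were added to avoid contamination of the preventive controls.
- **Annexure 4, on the earlier study:** among the reasons offered for improvement in the control group, "The NGO workers (CNO/CNP) adopted and used specific messages from instruction of our health assistants at the field level".

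**The concern.** Hypothesis (b) is one of only two hypotheses, and it is about persistence once education has stopped. The adaptation section permits education to continue under other staff from the point at which it is supposed to stop. The protocol thus holds two meanings of sustainability: an effect that lasts without education, and an effect maintained by routine CNP counselling. They call for different designs and support different programme decisions.

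The two possible exposures act in opposite directions. Continued education in LINE CNCs would make the effect look more durable than it is. Replication in no-education CNCs would shrink the difference between LINE and no education in the mildly malnourished children and the well-nourished infants.

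**Working it through.** **1. The passages side by side**

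| Months from start of education | Hypothesis (b) and time frame | Adaptation section |
|---|---|---|
| 1–3 | education, intense phase | no CNP role in delivery stated |
| 4–6 | education, reinforcement phase | adaptation begins: learning, time planning, standardization of sessions |
| 7–12 | observation, no intervention | where CNPs have time, they have by now taken over the health assistants' work and replicate it |

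I read the absence of intervention as absence of the study's education package, since ordinary project activities continue everywhere. Even so, the last row conflicts: the work taken over is delivery of that package.

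**2. What the condition does.** Takeover occurs only where a CNP has time. Exposure during months 7–12 is then neither zero nor assigned, and CNCs whose CNPs have spare time may differ from the others in ways related to growth. A LINE child whose status holds at month 12 may show persistence, continued education or both. Among the moderately malnourished there is no untreated group to help separate these (Table 1 of the protocol has only the two education arms).

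**3. Control exposure: an illustration.** The protocol gives no rate of exposure, so this shows only what would follow.

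- Plan's figure: 121 mildly malnourished children per group for a 20-point difference. The two rates are not legible. Assuming 0.50 and 0.30, the formula given for the management groups yields (0.50 × 0.50 + 0.30 × 0.70) / 0.20² × 10.5 = 120.75, which rounds to 121.
- Effective size per group: 190 × 0.9 / 1.5 = 114, after 10% dropout and the plan's design factor of 1.5.
- If k of the 8 no-education CNCs receive the package with full effect, the control rate is 0.50 − 0.20 × k/8, against 0.30 under LINE.
- Power = Φ{(d√n − 1.96√(2p̄q̄)) / √(p₁q₁ + p₂q₂)}, where n = 114, d is the difference between the two rates and p̄ is their mean.

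| k of 8 exposed | Control rate | Power |
|---|---|---|
| 0 | 0.500 | 87% |
| 1 | 0.475 | 78% |
| 2 | 0.450 | 65% |
| 4 | 0.400 | 35% |

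This concerns comparisons made after replication has begun. A comparison at the end of month 6 is less threatened.

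**4. Does staffing force takeover at month 6?** Health assistants: 20 × 102 × 18 months = 36,720. Supervisors: 4 × 206 × 18 = 14,832. Both equal the budget lines, so both groups appear to be paid for all 18 months. The earlier study also followed its children for three months in the absence of intervention, so such a period has been run before.

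**The case against.** The strongest reply is that takeover is only a possibility. It depends on CNP time, its details are still to be agreed with the implementing NGO, and CNP adaptation and CNP time constraints are themselves listed outcomes. The sentence about regular counselling is a loosely worded reply to an outside reviewer and does not say when or where counselling takes place. The 8 CNCs were added expressly to avoid contamination and are described as receiving no education. All of this is correct. It means that the observation period is put at risk and left undefined, not certainly lost, and that control exposure is an inference. It does not remove the conflict, because a conditional, unassigned takeover is still permitted in months a hypothesis requires to be free of it.

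A reader might also infer four stronger points that the protocol does not support:

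- **That measurement ends at month 6**, from "Weight and length will be taken each month for a period of 6 months". The Project Summary follows its account of the observation phase with recording of weight and length gain, outcome 9 covers nutritional status in that phase, monthly growth-monitoring data carry no six-month limit, and Data Analysis treats observation separately.
- **That intensive and less intensive education converge from month 4.** Only adaptation starts then, and the frequency tables keep the two reinforcement schedules distinct. A CNP taking over would on its face inherit that CNC's assigned intensity.
- **That the earlier study's control improvement, given as 18% in the Background and 30% in Annexure 4, measures contamination.** Annexure 4 offers four possible causes, including recovery after a flood and the harvest season, and apportions nothing.
- **That control exposure biases the comparison of the two intensities.** The no-education CNCs serve only the preventive comparison.

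**Conclusion.** The contradiction stands. The statement of hypothesis (b), the adaptation section and the reply on sustainability cannot all be followed. Where takeover occurs, the month-12 result would describe maintenance under CNP-delivered education and could not be attributed to persistence of the LINE effect. Up to all six observation months are open to this. How many would be affected, and in how many CNCs, cannot be derived from the protocol.

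Exposure of the 8 no-education CNCs is credible, because they share unions with education CNCs, are not excluded from replication, and the earlier study named this route. It is not stated to happen. The power figures rest on assumed rates of 0.50 and 0.30, the plan's design factor and dropout, and full effect in exposed CNCs. The comparison of the two intensities at the end of the intervention is not shown to be damaged.

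**What to change.** Reconcile the three passages before the study starts, in one of two ways:

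1. State in the adaptation section that CNPs and CNOs do not take over education sessions in the study CNCs before the month-12 measurement. CNP training and time mapping may proceed. Hypothesis (b) then stands as written.
2. If takeover must go ahead at month 6, restate (b) as sustainment with CNP-delivered education, and record the number of CNP-delivered sessions per CNC throughout observation so that the exposure can be described.

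In either case, state that no replication takes place in the 8 no-education CNCs before month 12, and align the reply on sustainability with the choice made.

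**Cost.** The first option delays CNP adoption in the study CNCs by about six months; the budget arithmetic suggests that staff pay does not stand in the way. The second keeps the adoption timetable but supports a narrower conclusion and adds a session record. Piloting adoption in CNCs outside the study would need training, supervision and data collection that the protocol does not describe, so it should not be assumed to be free.
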